BfArM	Federal Institute for drugs and medical devices (Bundesinstitut für Arzneimittel und Medizinprodukte)
BL	Burkitt lymphoma
BTK	Bruton's tyrosine kinase
cART	Combination antiretroviral therapy
CAR-T-cell	Chimeric antigen receptor T-cell
CCC	Comprehensive Cancer Center
CDC	Complement dependent cytotoxicity
CLL	Chronic lymphocytic leukemia
CNS	Central nervous system
COO	Cell of origin
CR	Complete remission
ctDNA	Circulating tumor deoxyribonucleic acid
DLBCL	Diffuse large B-cell lymphoma
DNA	Deoxyribonucleic acid
DOR	Duration of response
DRST	German Registry for Stem Cell Transplantation
GDPR	General data protection regulation
DSHNL	German study group for highly malignant non-hodgkin lymphomas
EBER-ISH	Epstein-Bar Virus encoded RNA in situ hybridization
EBMT	European Group for Blood & Marrow Transplant Research
EBV	Epstein-Barr Virus
EC	Ethics committee
ECOG	Eastern cooperative oncology group
eCRF	Electronic Case Report Form
EMCL	European mantle cell lymphoma registry
FL	Follicular lymphoma
FLIPI	Follicular lymphoma international prognostic index
G-BA	Federal joint committee (Gemeinsamer Bundesausschuss)
GCB	Germinal center B-cell
GLA	German Lymphoma Alliance

GLA-R	German Lymphoma Alliance-Registry
GLSG	German low grade lymphoma study group
HDT	High-dose therapy
HIV	Human immunodeficiency virus
HIV-HL	HIV-associated Hodgkin lymphoma
HL	Hodgkin lymphoma
IC	Informed consent
IMBEI	Institute of Medical Biostatistics, Epidemiology and Informatics
IMiDs	Immunomodulatory imide drugs
IPI	International prognostic index
IPS	International prognostic score
IQWiG	Independent Institute for Quality and Efficiency in Health Care (Institut für Qualität und Wirtschaftlichkeit im Gesundheitswesen)
IZKS	Interdisciplinary Center for Clinical Trials
LKR	Landeskrebsregister
MCL	Mantle cell lymphoma
MH	Morbus Hodgkin/Hodgkin's lymphoma/Hodgkin's disease
MIPI/MIPI-c	Mantle Cell Lymphoma International Prognostic Index
MM	Multiple Myeloma
moAB	Monoclonal antibody's
MRD	Minimal residual diseasedisease
mTOR	Mammalian target of rapamycinrapamycin
MYC	MYC proto-oncogene
MZL	Marginal zone lymphomalymphoma
NHL	Non-Hodgkin lymphoma
NOS	Not otherwise specified
ORR	Overall response rate
OS	Overall survival
PBL	Plasmablastic lymphomalymphoma
PEL	Primary effusion lymphomalymphoma
PD	Progressive disease
PDX	Patient-derived xenograftxenograft
PET	Positron emission tomography
PI3K(i)	Phosphatidylinositol 3-kinase (inhibitor)
PFS	Progression free survival
PLHA	People living with HIV/AIDS
POD12	Progression of disease within 12 month
POD24	Progression of disease within 24 month
PR	Partial response
PTLD	Post-transplant lymphoproliferative disorder
QoL	Quality of life
RKI	Robert Koch Institute
SC	Steering committee
SCT	Hematopoietic stem cell transplantation

SD	Stable disease
SOP	Standard operating procedure
T-NHL	T-cell non-Hodgkin lymphoma
WHO	World health organization
WP	Working Party

1. Overall Background

Real world evidence has become a widely accepted source of information for various cancer entities to add to or partly substitute the result from controlled clinical trials. In detail, real world data collections provide information on therapeutic pathways, use of novel treatments, treatment algorithms and impact of these therapies on the overall/more general patient population (1, 2). Special benefits are the long-term collection of data over the entire disease course and the integration of information of literally all patients without inherent limitations of controlled trials. In addition, long-term collections allow understanding of the change of treatment patterns over time, survival trends in different patient generations, trends in participation in clinical trials and their impact on survival, quality of life (QoL), health care utilization and potentially complications and limitations of multiple treatments (3).

In this intent, the German Lymphoma Alliance will establish a clinical, non-interventional, retro- and prospective clinical registry. All patients with malignant lymphatic malignancies (except chronic lymphocytic leukemia (CLL), morbus hodgkin (MH) and multiple myelom (MM)) and related lymphoproliferative diseases can be included into the registry.

The current lymphoma landscape - the impact of Real World Evidence

Major improvements of biological understanding and classification of malignant lymphomas has been made over the last decades. This has resulted in a continuous fragmentation of disease entities with increasingly smaller samples sizes, which in turn limits the chance to study all entities prospectively in distinct trials.

At the same time, a substantial number of therapeutic improvements were established based on controlled clinical trials. The full impact on routine care, however, can hardly be detected within these studies. In general, this limitation is related to patient selection, limited follow-up and interference with routine treatment strategies. Furthermore, complex and selective inclusion criteria, the overrepresentation of young and fit patients and the underrepresentation of patients treated at private institutions frequently results in inferior outcomes of treatments in routine use—in terms of efficacy and toxicity. In addition, some treatment options were approved on small phase II trials lacking a randomized comparison to standard options, whereas in other controlled trials standard treatments were used, which would no longer be considered the primary choice of treatment. Finally, long-term effects on quality of life and impairment of a variety of dimensions, as well as late toxicities can only be followed in a limited fashion within clinical research projects. All these limitations highlight the importance of real world data, which in part can compensate for the lack of knowledge, which exists if only controlled trials in distinct therapeutic scenarios are considered.

Integration of registries

Currently, several lymphoma registries are already implemented in Germany focusing on distinct entities (e.g. follicular lymphoma (FL) or mantle cell lymphoma (MCL)), using different documentation formats and platforms, requiring different informed consent forms and have redundant administrative and supportive structures. It is of great importance to secure the data which already have been obtained on the one hand, but develop a common platform, which allows to significantly reduce workload, expenses and required structures. To accomplish this unification (on one platform or an established exchange format) is a central part of the GLA-R.

Further aspects

Ideally, the collection of clinical data will be accompanied by collection or at least registration of a catalog of biological samples for the patients included in the registry, inclusion of prospective patient reported outcomes or theoretically even biometric information as provided by e.g. wearables.

There will be harmonized data sets for all patients with additional entity-specific additions.

In addition, using appropriate statistical instruments like propensity score matching or weighting and regression modelling, valid comparison to data from clinical trials can be made (4). Furthermore, long-term follow-up of clinical trials and further research projects can be managed via registries.

Regulatory considerations

Whereas clinical registries cannot provide the data depth and all quality parameters of controlled clinical trials, it is of great importance to comply with current regulations and suggestions for the conduct of such data collections to standardize results and leverage acceptance of the results obtained (3). Recently, the German Institute for Quality and Efficiency in Health Care (IQWiG) has published a which covers clear instructions for quality measures for research done in clinical registries to comply with requirements for acceptance of respective results (5). To comply with these regulations will be a major effort of the GLA-R to safeguard the future value of the project.

Non-interference with treatment

Within the registry predetermined treatment concepts are not evaluated in terms of indication and appropriateness. Neither is any treatment suggested, nor will any advice be given for the treatment of an individual patient.

2. Aims of the Registry

The following not exclusive aims of the registry have been defined, further aspects may be added at any time:

On an organizational level

- To build an overarching platform for the collection of data of patients with malignant lymphoma
- To integrate currently active registries within the network of the GLA
- To establish appropriate tools for entities not followed currently
- To establish an appropriate structure to conduct projects for:
 - o Representation of health care utilization
 - o Therapy comparison, Evaluation of Efficacy, and benefit in the routine
 - o Analysis of epidemiological differences and correlations
 - o Registry based studies
 - o Routine Practice Data Collection (e.g. Anwendungsbegleitende Datenerhebungen, AbD)

Establish a platform for linked biologic analyses

- On primary materials and potentially on prospectively sampled materials

To establish a data exchange platform

- With other academic complimentary registries
- To develop a tool to integrate data from clinical trials
- To establish long-term follow-up of clinical trials
- To integrate currently available data from earlier trials as benchmark.

To offer an information resource platform

- For treating physicians, pathologists, researchers
- To support on demand e.g. regulatory bodies
- To interact with patient advocacy groups.

3. Patient selection

All patients with the diagnosis of a malignant lymphoma are eligible in general (exceptions are stated in inclusion criteria chapter 3.1). However, data entry depends on the development status of the registry, e.g. if an appropriate module for the entity already has been activated.

It is especially encouraged, to include patients which would not be eligible to participate in clinical trials due to their age, underlying health conditions or comorbidities, reflecting the daily clinical routine.

Patients can be included regardless of their individual treatment time point during the disease course. If available, all relevant data of the prior disease course will be collected retrospectively.

Application will be made to accept the entry of patients who already have deceased at the time of the initiation of the registry. Restrictions may apply to specific entities, depending on coverage within the registry.

3.1. Inclusion criteria

- Malignant lymphoma (except for Hodgkin's disease (MH) without concomitant HIV infection, multiple myeloma (MM) and chronic lymphocytic leukemia (CLL)) or related lymphoproliferative disease e.g. Castleman's disease
- Informed consent
- ≥ 18 years at the time of consent

There are no exclusion criteria.

4. Objectives

4.1. Overall scientific objectives

It is the purpose to understand efficacy, treatment algorithms, change of treatment patterns, influence of distinct treatment on the subsequent treatment lines, long-term results of clinical research projects, pattern of resistance, quality of life as well as health care utilization. Subgroup analyses will be performed e.g. to understand the influence of specific novel treatment approaches and the fate of distinct risk populations, as defined by clinical, biologic or genetic characteristics.

4.2. Primary Objective

Disease specific: Understand the disease course of different lymphoma entities with the use of different treatment modalities or different treatment sequencing.

Treatment specific: Understand the results and impact of specific treatment methods.

4.3. Secondary Objectives (non-exclusive)

Note: Additional objectives might be added depending on new scientific questions or results

- Understand scope of responses to sequentially applied treatments
- Collect real world data on treatments used
- Collect real world data on progression free survival

- Collect real world data on overall survival
- Collect real world data on healthcare resource utilization (project-specific)
- Develop prediction model for selection of drugs
- Analysis of treatment schedule algorithms
- Long-term follow-up of clinical trials
- Analyze treatment specific adverse events (project-specific)
- Evaluation of prognostic scoring system in the population of subpopulations
- Evaluation of impact of comorbidity scores on outcome
- Evaluation of Quality of Life (project-specific)

Note: QoL analysis are highly relevant and attractive, however cannot be analyzed on a retrospective fashion and therefore will be collected prospectively only from selected patient populations or within distinct research projects.

5. Statistical Analysis

The registry data will be used to evaluate commonly accepted parameters for the description of disease risk, treatments received, response to treatment, pattern of relapse, relapse strategies etc. Non-exclusive parameters are:

Cohort characterization:

- Demographics
- Relevant concomitant diseases
- Disease presentation
- Histology, subtype, clinical and molecular risk factors
- Stage, symptoms, including date of assessment
- Evaluation of risk scores according to current recommendations (adaptive)

Treatment characteristics and outcome:

- Type of treatment in first or subsequent treatment lines: antibody, chemotherapy, HDT, use of novel agents, radiotherapy, use of maintenance, adherence, cellular therapies
- Response to different treatment lines: Quality of remission (CR, PR, SD, PD, n.k.) and the method of detection (clinical, radiographic, PET, MRD etc.)

- Remission duration and survival analysis: DOR, ORR, PFS, OS, cause of death, after first-line treatment and subsequent lines, proportion of early relapses (e.g. POD12, POD24) and impact on results
- Pattern of relapse, method for relapse detection
- Identification of treatment pathways in the entire population and in subgroups (age, risk, growth pattern, period of treatment etc.)
- Reasons for discontinuation of treatment
- Exploratory analysis of above-mentioned parameters in relevant subgroups, e.g. age (discrimination by age itself and fitness for intensive treatment), clinical and genetic risk profile etc.

6. Organizational Structure of the Registry

This pan-lymphoma registry represents a core scientific project of the German Lymphoma Alliance e. V. This implies that all key decisions in respect to the registry are to be discussed and decided within the assembly of the Alliance. For practical reasons, however, a steering committee (SC) and a GLA-R Delegate will be assigned to develop or continue the project for the Alliance in liaison with the board of the GLA, e.g. as responsible person for submission to ethics committee and other relevant regulatory bodies, if required.

The following regulations apply:

6.1. Governance

Contracting for funding (either public or with e.g. companies) is awarded by the GLA or a “for profit” branch of the “e. V.”, whatever is appropriate. The GLA will mandate the conduct of the registry to an appropriate partner (Interdisciplinary Center Clinical Trials (IZKS) and Institute of Medical Biostatistics, Epidemiology and Informatics (IMBEI)), which is responsible for technical facilitation, data hosting and quality management, regulatory, and biometry but does not work scientifically on its own intent on the data. However, analysis on demand can be mandated by the GLA, if required. The GLA establishes a steering committee, which consists of the WP registry, members of disease specific WP and qualified researchers, and supervises the GLA-R and advises on the specific projects. Importantly, the steering board will work to established rules for the conduct of registry studies within the GLA-R, e.g. how to evaluate scientific projects, whom to grant access, publication of results, cooperation with non-academic institutions etc. The following diagram summarizes this structure.

[figure not shown]

Figure 1: Organizational structure of the registry

6.1.1. Composition of the Steering committee

The following representatives are involved

- Organization/Speaker of the Board: GLA-R Delegate ([name], 2023)
- Further members:
 - Registry Delegate of the GLA
 - Delegate of WP Biometry and Bioinformatics
 - Delegate of WP Diagnostics and Biology
 - Lead of current GLA-registries (MZL/FL, T-NHL, MCL)
 - Delegate of central services (IMBEI/IZKS)
 - Up to 3 Delegates of the group with expertise in the field
- Ombudsman
 - President of the GLA (or President elect as deputy)

6.1.2. Meeting of the Steering committee

The SC will meet once a year in a personal meeting, in which the speaker of the board will present the current status of the entire project.

Up to four virtual meetings will be scheduled to discuss specific projects or actual questions.

6.2. Data Ownership

The database will be owned by the GLA. The transfer of rights to the GLA will be regulated by the informed consent; each patient has to sign prior to participation. For pre-existing data bases migration to the GLA-R is preferred with privileges (e.g. right to veto of data usage, (co-)authorship) for founding institutions for a distinct period (e.g. 10 years in general) or individual regulations, which may apply. Appropriate regulations for the transfer of data from existing registries and former clinical trials into the GLA-R will be made in accordance with applicable law.

Alternatively, and especially during set-up of the registry, data sharing with existing registries might optionally be used for scientific exchange and might be the preferred option prior to final transfer of registry data.

6.3. Data Sources

The GLA-R integrates available data from various sources. Non-exclusive examples are

- Data entered from GLA partner sites upon informed consent of patients with lymphoma in GLA-R (retrospective and prospective).
 - o data from patients which have deceased can be entered depending on the specific regulations at the distinct participating sites -depending on EC-approval at the respective sites
- Data from already existing lymphoma specific registries, e.g. MZL-registry, FL-registry, T-NHL-registry, (E)MCL-registry and all others should finally be migrated into the GLA-R.
- Data from former clinical research projects of GLSG, DSHNHL and other preceding trial groups after regulatory clearance.
 - For the transfer of data from ancient trials of precursor trial groups (e.g. GLSG, DSHNL) specific regulations will be defined by the WP Biometry.
- Data transferred from other non-lymphoma specific registries as procedure related registries (e.g. DRST, EBMT), national cancer registries or clinical cancer registries of Comprehensive Cancer Center (CCC) or equivalent.

- Data of upcoming GLA-trials, which mandatory should be transferred in a suitable form into the registry.

The migration of data will be dependent on regulations which will be defined to respect current legal or data protection regulations.

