9.2. Informed consent

Participation in this project is entirely voluntary. There is no direct impact on the treatment of the individual patient. The GLA-R informed consent form will be distributed to patients eligible for this registry and still alive. In addition, patients will receive all relevant information on data protection in its latest version and the potential use of their data for the different analyses, including shared analyses with network partners and commercial cooperators.

Historical patient data will be entered if appropriate consent exists by hospital and/or ethic regulations.

The informed consent to participate in the registry may be withdrawn by the patient verbally or in written form at any time during the trial. The patient must not entail any disadvantage therefor or be coerced or unduly influenced to continue to participate. Furthermore, the patient is not obligated to disclose reasons for the withdrawal of the consent.

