9.3. Data protection

Within the registry, the applicable data protection is respected. The EU Regulation 2016/679 of the European Parliament and the Council GDPR, which has been in force in Germany since May 2018, defines various legal aspects of data protection. According to Article 6(1) (a), the processing of personal data is permitted if "the data subject has given his or her consent to the processing of personal data for one or more purposes". Article 5(1) (b) also states that "personal data may be used only for specified, explicit and legitimate purposes and may not be used for other purposes not agreed upon; the further use of data intended for archives in the public interest, for scientific or historical research projects or for statistical purposes is not incompatible with the original purposes pursuant to Article 89(1)". Article 7(1) further states that "if the use of the data is based on consent, the person responsible must prove that the individual concerned has given consent to the use of personal data".

In order to comply with the provisions of the GDPR, the collection of data in the registry is only possible if written consent has been obtained from the patient, if not addressed in special regulations (e.g. deceased patients).

If consent is given, the collected data are entered into an access-protected database. This database does not contain any information that allows clinical data to be assigned to an individual person. Instead, all data are assigned to a clearly defined alphanumeric pseudonym that contains neither parts of the name nor the date of birth.

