9.5. Trusted third party

Patient identifying data (e.g. surname, first name, date of birth and address) will be collected and stored separated of the medical data in the trusted third part in safe custody. There will be an organizational separation from other registry operations. Only trained and authorized personnel will have access to the personal identifying data. The disclosure to any third party is excluded.

10. Data reports

A summary report of the clinical data of the registry is prepared annually. The following analysis will be performed by the institution to which the conduct of the registry will be delegated on behalf of the GLA.

- Number of patients included into the registry and in the different lymphoma subtypes
- Patient characteristics
- Cumulative entity overall survival, depending on age, sex

Each center has the option to receive the data of their own patients entered on a per center analysis (with and without benchmark data). All members of the registry have access to e.g. the annual analyses and other appropriate materials. If used, the GLA-R needs to be referenced.

Note: As of 2023 IZKS/IMBEI Mainz are responsible for the provision of the annual analysis.

For each lymphoma entity-specific data points or research questions may be predefined which will be specific to the respective part of the GLA-registry. The basis for these data points will be revised annually by the speakers of the respective working parties to keep the data base updated for the most recent development. Changes to the item list will be reported on the website of the society. Reminders will be sent by the project coordination in summer of the preceding year, to be discussed at the annual meeting and then to be integrated into a regular database release in Q1 or Q2 of the subsequent year.

Primary data analyses will be provided in Q2 to the WP for discussion and distribution, in general for presentation at the annual meeting.

11. Role of funding sources

There is no single funding source to cover the costs of the registry. For the start of the project the GLA e. V. provides funding to establish the data base and facilitate registry coordination and management. In addition, cooperation projects with industrial partners have been defined to cover remaining project costs. As of Q1 2023 funding for the first 3 years is covered.

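### Entry of already-deceased patients depends on each site's rules while living patients may enter at any point of the disease course, so survival estimates that include prevalent or retrospective records are biased by an amount that differs by site

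*Protocol*

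**What the plan says.** **Who may enter.** Section 3.1 lists "Informed consent" as an inclusion criterion without exception, and section 6.2 says "each patient has to sign prior to participation". Section 9.2 adds: "The GLA-R informed consent form will be distributed to patients eligible for this registry and still alive". Section 9.3 supplies an exception: data collection "is only possible if written consent has been obtained from the patient, if not addressed in special regulations (e.g. deceased patients". Section 6.3 leaves deceased patients to the sites: "data from patients which have deceased can be entered depending on the specific regulations at the distinct participating sites", with ethics approval at the site. Section 3 is narrower in scope: "Application will be made to accept the entry of patients who already have deceased at the time of the initiation of the registry".

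**When they may enter.** Section 3 accepts patients at any treatment time point. Section 8.5 collects the course up to registration retrospectively and is open to historical data as a control.

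**What is reported.** Section 8.9 estimates OS by Kaplan-Meier. It names no time origin and does not mention delayed entry. Section 10 promises annual OS per entity by age and sex, and adds: "Each center has the option to receive the data of their own patients entered on a per center analysis (with and without benchmark data". Neither section separates records by vital status at entry or by the site's entry rule.

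**The concern.** A patient diagnosed before registration and still alive can be consented and entered anywhere. The same patient, if dead, can be entered only where local rules allow. The outcome thus decides inclusion, and decides it differently by site.

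A site that cannot enter its dead contributes survivors whose time from diagnosis to registration could not have contained a death; counting that time as time at risk inflates OS. A site that enters its dead has no such inflation, but its estimate is right only if dead and living are captured equally completely, which the protocol does not require.

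At stake are the annual entity OS, any historical control built from these records, and the centre benchmark if it uses OS. A centre could look better or worse than its neighbour because of its ethics committee's decision, with no difference in care.

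**Working it through.** The protocol states no OS target, power or event count on this point, so there is no figure of the plan's own to reproduce. The check asks how far the entry rule alone can move Kaplan-Meier OS.

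**Inputs**
- True 2-year OS: 62%, the protocol's figure for DLBCL in the HIV cohort (section 12.3.2), used only as an illustration; 50% and 80% also tried.
- Follow-up: 3 years after opening (assumption, from the 2023–2025 first phase in section 12.1.4).
- Look-back for prevalent patients: 2, 5 or 10 years, uniform (assumption).
- Prevalent share: 0, 25, 50 or 100% (assumption); the rest are diagnosed during the 3 years after opening.
- Survival exponential and identical at all sites; OS counted from diagnosis (assumption).
- Site A enters all its dead and all its living; site B enters no dead. The pool is half of each.

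**Closed form for the all-prevalent case (62%, 5-year look-back)**

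The hazard is λ = −ln(0.62)/2 = 0.2390 per year, so e^(−5λ) = 0.3027. Everyone has at least 3 years of potential follow-up from diagnosis, so nobody is censored before 2 years. Naive Kaplan-Meier at site B is then the share of entered patients who live beyond 2 years:

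- Alive at opening: (1 − 0.3027)/(5 × 0.2390) = 2.917/5 = 0.583 of all diagnosed, so 42% are already dead.
- Alive at opening and surviving beyond 2 years: [2 × 0.62 + (0.62 − 0.3027)/0.2390]/5 = 2.568/5 = 0.514.
- Site B: 0.514/0.583 = **88%**, against a true 62%.
- Half-and-half pool: (0.62 + 0.514)/(1 + 0.583) = **72%**.

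**Simulation, 60,000 patients per scenario (true 62%, 5-year look-back)**

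| Prevalent share | Site A | Site B, plain KM | Pool | Site B, delayed-entry KM |
|---|---|---|---|---|
| 0% | 62.0% | 62.0% | 62.0% | 62.0% |
| 25% | 62.0% | 68.0% | 64.9% | 62.2% |
| 50% | 62.2% | 74.3% | 67.4% | 62.3% |
| 100% | 62.2% | 88.0% | 71.6% | 62.1% |

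The 100% row agrees with the closed form. The gap between identical centres is 6, 12 and 26 points at 25, 50 and 100% prevalent.

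**Range over the grid (prevalent share 25–100%)**
- Smallest gap: 82.7 − 80.1 = 2.6 points (true 80%, 2-year look-back, 25% prevalent); pooled excess 81.3 − 80.1 = 1.2.
- Largest gap: 84.1 − 50.0 = 34.1 points (true 50%, 10-year look-back, 100% prevalent).
- Largest pooled excess: 60.2 − 50.0 = 10.2 points (true 50%, 5-year look-back, 100% prevalent).

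**Direction.** Let an all-prevalent site enter all its dead but only a fraction q of its living. Its 2-year estimate is (0.62 − 0.514 + 0.514q)/(0.417 + 0.583q), which gives 44% at q = 0.3, 51% at q = 0.5 and 59% at q = 0.8, all below 62%.

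**Repair.** Delayed-entry Kaplan-Meier on living entrants returns the truth within about 1.3 points over the whole grid. The larger deviations occur where all patients are prevalent and early risk sets are small.

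**The case against.** The strongest reply is that much of this belongs to the analysis plan. Time origin, left truncation and stratification by entry type are commonly left there, and that plan is not shown. Section 8.9 allows extensions of the Cox model, section 7.1 requires a statistician and an analysis plan for each project, and the audit trail (section 8.10) time-stamps entries. This stands for living prevalent patients, whom delayed entry repairs. It does not stand for patients entered after death: they have no time at risk after entry, so their records inform survival only if the site's cohort is complete. Completeness is set by the enrolment rule, and no later analysis can recover an unknown share of missing deaths.

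Four stronger readings are tempting, and the document does not support them.

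- *Registry OS is invalid as a whole.* Patients registered at diagnosis are unaffected, and with no prevalent records the bias is zero. An all-prevalent model with true 5-year OS of 60% can be made to show 80% at a survivors-only site and 47% at a site entering all its dead but half its living. That 33-point spread rests on a registry without incident patients and on a hypothetical site type. The protocol is also prospective, and section 12.1.5 expects 500 large B-cell entries a year.
- *Consent and deceased entry flatly contradict each other.* Section 9.3 states the exception and section 9.2 limits the form to the living. What remains is that 3.1 and 6.2 do not carry the exception.
- *Section 3 steers enrolment by prognosis.* "It is especially encouraged, to include patients which would not be eligible to participate in clinical trials" is an encouragement, not a preference over others. Section 1 explains the aim of countering over-representation of young and fit patients.
- *The centre benchmark compares OS.* Section 10 does not name the measure. OS appears just above it in the list of annual analyses, so the inference is natural but not stated.

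**Conclusion.** The point holds in a bounded form. Site-dependent entry of the dead, combined with open entry of the living at any disease stage, makes inclusion of prevalent patients depend on vital status in a way that varies between sites. Plain Kaplan-Meier OS from diagnosis is biased to the extent that such records are included.

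Under the assumed ranges, the gap between identical centres is about 3 to 34 points and the excess in a half-and-half pool about 1 to 10 points. The sign can reverse where the dead are captured better than the living. These figures rest on exponential survival, an assumed look-back and an assumed prevalent share. The protocol gives neither of the last two, so the actual size cannot be fixed.

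This should be corrected in the protocol because the missing element, a completeness rule for deceased entries, is an enrolment matter.

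**What to change.** 1. Record for each patient the registry entry date and an entry type: registered at diagnosis, prevalent and alive, or deceased at entry.
2. In all survival analyses, let living prevalent patients join the risk set at their registry entry date (delayed-entry Kaplan-Meier or Cox). This assumes that, given survival to entry, the time of entry is unrelated to prognosis; registration prompted by relapse would strain that and should be examined.
3. Use deceased-at-entry records for survival and historical controls only from sites that enter every consecutive eligible patient of a stated diagnosis window regardless of vital status, and analyse those complete cohorts from diagnosis. Elsewhere use such records in descriptive tables only.
4. Base any centre survival benchmark on patients registered at diagnosis or on the delayed-entry analysis.
5. Carry the section 9.3 exception into sections 3.1 and 6.2, and reconcile section 3 (dead at registry initiation) with section 6.3 (no time limit).

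Steps 2 and 3 belong together. In the all-prevalent model with true 5-year OS of 60% (diagnoses over 5 years before opening, 1.5 years of further follow-up), pool equal thirds of sites entering none, half and all of their dead. Plain Kaplan-Meier gives 69%. Dropping the deceased records at the incomplete sites, while still counting their living patients from diagnosis, raises this to 72%. With delayed entry for the living at those sites and the complete sites analysed from diagnosis, it returns 60%.

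The cost is protocol wording and two data items, if they are not already on the item list, which is held outside the protocol. Some deceased records will not be used for survival, and delayed entry loses some precision early in follow-up.
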